Study parameters: Anthropometric parameters include body height, body weight, segmental circumferences, somatotype, body shape, muscle CSA and muscle volume of the lower limbs. Anthropometric parameters will be assessed by means of HMF fitting in combination with data from 3D body scanning and anthropometric measurements according to ISAK standards. Changes in CSA of the hamstrings and quadriceps will be compared between HMF and data from ultrasound before and after strength training intervention. Strength- and training-specific parameters include joint motion, joint acceleration, total joint moments, repetition count, 1RM and H:Q ratio. Strength- and training-specific parameters will be assessed by means of biomechanical analysis using data from optical motion capture and the *iOS Strength Control app*, and compared against data from isokinetic strength tests as gold standard. Additionally, data from MRI of the lower limbs will be acquired in a sub-group of 12 participants (6F, 6M), who will be scheduled for one visit to the imaging facilities of the Swiss Centre for Musculoskeletal Imaging (SCMI) at the Balgrist Campus Zurich. The SCMI provides a highly specialized open access musculoskeletal imaging infrastructure, with a 7T Magnetom Terra and 3T Magnetom Prisma MRI device (Siemens) that can be booked per hour, including imaging support through a professional radiographer. Scan parameters are defined in line with previous research by our group [21]. Participants will be reimbursed for travelling costs.

This is a single-centre study that will be conducted at the research facilities of the ZHAW.

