## 2 PROJECT OBJECTIVES AND DESIGN

### 2.1 Hypothesis and primary objective

Hypothesis: It is hypothesized that advanced subject-specific musculoskeletal modelling in combination with mobile monitoring technology as embedded in the iPhone and Apple Watch allow for accurate prediction of changes in muscle strength and muscle size in the lower limbs following an 8-week strength training intervention of key muscle-tendon groups associated with knee joint stability.

Primary Objective: Prediction of changes in muscle strength in the lower limbs due to different strength training volumes by means of the advanced computational modelling, biomechanical analysis and mobile monitoring technology. Of particular interest is the prediction of 1RM and the prediction of the ratio between hamstrings and quadriceps strength (H:Q ratio) compared against isokinetic strength tests as gold standard. Research has clearly shown that the quantification of 1RM is fundamentally important when it comes to the design of safe and efficient resistance training programs. Improved accuracy in the 1RM prediction compared to preliminary studies (i.e. mean %error of 0.27% in 60% and 7.81% in 80% 1RM assessment [29-34]) is expected through the consideration of data from optical motion capture as well as the additional consideration of subject-specific musculoskeletal anatomy from computational modelling.

Secondary Objective: Assessment of changes in muscle size in the lower limbs due to different strength training volumes using the HMF technique. Of particular interest is the prediction of muscle volume using the HMF technique compared against data from MRI as gold standard, as well as the prediction of adaptation in hamstrings and quadriceps CSA due to the strength training intervention using HMF versus data from ultrasound, respectively. Improved accuracies in the assessment of muscle size compared to preliminary studies (i.e. more than 70% accuracy in muscle volume [22]) are expected through the additional data from anthropometric measurements and the matching of generic model to the study-specific population group including gender.

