### 2.2 Primary and secondary endpoints

Primary Endpoint: Changes in muscle strength in the lower limbs following the 8-week strength training intervention of the lower limbs in three study groups with different training volumes. The two strength-specific primary outcome parameters are: 1RM and H:Q ratio. Changes in 1RM and H:Q ratio will be derived using the *iOS Strength Control app* and biomechanical analysis before and after the strength training intervention. Primary outcome parameters will be compared between the three study groups in relation to training volumes (Group#1: no training, Group#2: 1 training per week, Group#3: 3 trainings per week). The accuracy in the prediction of 1RM and H:Q ratio will be compared with data from isokinetic strength tests as gold standard.

Secondary Endpoint: Changes in muscle size of the lower limbs following the 8-week strength training intervention of the lower limbs in three study groups with different training volumes. The two secondary outcome parameters are: muscle volume and CSA. Changes in muscle volume and CSA will be derived using the HMF technique in combination with data from 3D body surface scanning and anthropometric measurements before and after the strength training intervention. Secondary outcome parameters will be compared between the three study groups in relation to training volumes (Group#1: no training, Group#2: 1 training per week, Group#3: 3 trainings per week). The accuracy in the derivation of muscle volume and CSA using the HMF technique will be assessed using data from MRI and ultrasound as gold standard.

Key baseline factors that will likely influence the primary and secondary endpoints are strength training experience and gender. The sample size and population group are specified to allow the analysis of gender-specific differences on study results. Thereby, the inclusion/exclusion criteria and study protocol, including a training-related questionnaire, are defined to minimize the bias of training experience.

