## 4 STATISTICS AND METHODOLOGY

### 4.1. Statistical analysis plan

Statistical analysis will be conducted with SPSS (SPSS v. 21, IBM, USA) after consultation with a statistician in line with previous research by our group.

For the Primary Objective, a repeated measures analysis of variance (ANOVA) will be conducted to assess statistically significant differences between the predicted values of 1RM and H:Q ratio from biomechanical modelling and mobile monitoring with the measured values from optical motion capture and isokinetic strength tests following the 8-week strength training intervention. A correlation analysis will be done to relate the strength-specific outcome parameters to the training-specific parameters for each study group. Principal component and factor analysis will be performed to identify correlations between strength-specific and training-specific parameters.

For validation of the HMF technique, we will follow the statistical methods of previous research by our group [21, 22] to assess the significance in the differences of muscle volume between HMF and MRI, as well as the difference of the predicted adaptation in CSA between HMF and ultrasound. The level of significance in the difference of muscle volume between HMF and MRI is expected to vary across muscle-tendon groups and gender. In particular, no significant differences were found in the predicted volume of semitendinosus and semimembranosus as part of the hamstrings between HMF and MRI in 5 children without CP (MRI 5.1 (0.91) versus HMF 5.0 (0.30) cm^3/kg, p-value >0.05) and in the predicted volume of the quadriceps, including vastus lateralis, medialis, intermedius and rectus femoris, in 6 children with CP (MRI 15.9 (3.20) versus

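### Optical motion capture is absent from the primary 1RM and H:Q prediction in the hypothesis and 4.1, an input to it in 2.1 and 2.3, and a reference in 4.1

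*Combined protocol and SAP*

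**What the plan says.** The plan describes the method under test in five places.

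- **2.1, hypothesis.** Subject-specific modelling is combined with phone and watch: "mobile monitoring technology as embedded in the iPhone and Apple Watch allow for accurate prediction of changes in muscle strength and muscle size". Motion capture is not named.
- **2.1, primary objective.** Better 1RM accuracy than in the preliminary studies "is expected through the consideration of data from optical motion capture as well as the additional consideration of subject-specific musculoskeletal anatomy". Here motion capture is an input to the 1RM prediction.
- **2.2, primary endpoint.** Changes in 1RM and H:Q ratio come from the iOS app "and biomechanical analysis before and after the strength training intervention". The data that feed the biomechanical analysis are not stated.
- **2.3, study parameters.** The list includes 1RM and H:Q ratio, and the method is given as: "Strength- and training-specific parameters will be assessed by means of biomechanical analysis using data from optical motion capture and the" iOS app, with isokinetic tests as the gold standard.
- **4.1, analysis plan.** The repeated-measures ANOVA compares "predicted values of 1RM and H:Q ratio from biomechanical modelling and mobile monitoring with the measured values from optical motion capture and isokinetic strength tests". Here motion capture stands on the reference side.

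Section 3.3 identifies the system as a 10-camera Vicon installation, recorded at the same time as the iPhone and watch data.

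**The concern.** The primary question is how accurate a prediction is, so the plan has to fix what goes into that prediction. It gives two answers that cannot both hold, and it gives motion capture a third role as comparator.

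The intended use makes this matter. Section 1.3 aims at assessment away from the laboratory and clinic. In Phase B, participants train in facilities of their own choice and follow their 1RM with the app, and no motion capture is specified there. Section 1.3 also says that the app's assessment of exercise execution and 1RM still needs development and validation. If the prediction uses Vicon data, that validation is not delivered, yet a favourable result could be reported as support for the phone-and-watch hypothesis. Leaving the choice open also allows the better-performing version to be selected once the data are seen.

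**Working it through.** The plan gives no figure on this point, so the check sets the sections side by side.

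**Step 1. Role of motion capture by section**

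| Section | Predictor | Reference | Role of motion capture |
|---|---|---|---|
| 2.1 hypothesis | Model + iPhone/Apple Watch | Not stated | None |
| 2.1 objective, expected accuracy | Adds motion capture and subject-specific anatomy | Isokinetic | Input |
| 2.2 | App + biomechanical analysis | Isokinetic | Unclear |
| 2.3 | Motion capture + app | Isokinetic | Input |
| 4.1 | Model + mobile monitoring | Motion capture + isokinetic | Reference |

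The clear conflict is between the hypothesis and 4.1 on one side and the expected-accuracy sentence and 2.3 on the other. Section 2.2 belongs to neither, because 2.3 describes biomechanical analysis as drawing on motion-capture data.

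**Step 2. What each reading would deliver**

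- *4.1 taken literally:* the predictor matches the hypothesis and both references are separate from it. The expected-accuracy sentence and 2.3 are then wrong.
- *2.3 taken literally:* the predictor contains Vicon data. The isokinetic comparison remains independent, but it measures the accuracy of a different method from the one in the hypothesis.
- *2.3 predictor with 4.1 reference:* the hypothesis is not tested, and the motion-capture part of the comparison sets a prediction partly against its own input. Agreement there is inflated by construction.

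**Step 3. Is a prediction free of motion capture analysed anywhere?** No section specifies an accuracy analysis that explicitly excludes motion-capture input. The app's 1RM values from Phase B have no accuracy analysis either.

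**Step 4. Can the two versions be separated?** For the data, yes. Section 3.3 has them recorded simultaneously, and section 7.2 lists watch IMU data and marker trajectories as separate source items. For the algorithms, this is not shown for both outcomes: section 1.3 gives the app's outputs as exercise type, repetition count and 1RM, and does not mention H:Q ratio.

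**Step 5. Can the effect on accuracy be sized?** No.

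- Section 2.1 gives two preliminary mean errors, 0.27% at 60% 1RM and 7.81% at 80% 1RM. They differ by a factor of 7.81 / 0.27 = 28.9.
- The expected improvement is credited jointly to motion capture and to subject-specific anatomy, with no split.
- The figures are errors in a 1RM level, whereas the endpoint is a change. A stable error would cancel between the two visits.
- The sample-size calculation does not help. Its effect size reproduces: (200.8 − 170.6) / √((21.4² + 19.0²)/2) = 30.2 / 20.24 = 1.49, against the stated 1.5. The stated 11 per group also reproduces as a two-group t-test at one-sided 0.025 and power 0.9 (10.40, rounded up). Both concern a training effect, not prediction accuracy.

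**The case against.** The best defence is that 4.1 governs the analysis, and 4.1 keeps motion capture out of the predictor. On that reading the planned result does address the hypothesis. This stands in part: the harm is conditional on 2.3 being followed. But no section gives 4.1 precedence, and the primary objective ties motion capture specifically to 1RM accuracy.

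A second defence is that the sentence in 2.3 covers several parameters together, including joint motion and joint moments, so motion capture might serve only those. That is possible for 2.3 alone. It does not explain the expected-accuracy sentence, which is about 1RM.

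Three stronger readings are tempting, and the documents do not support them.

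- *The plan claims accuracy for phone and watch by themselves.* It does not. The hypothesis is about modelling combined with mobile devices. The subject-specific model also relies on a body-surface scanner and anthropometry at the study site, so removing Vicon does not make the method fully portable.
- *The overstatement can be put in kilograms from the 7.81% error.* That would ignore the 0.27% figure, need an invented share for motion capture, and use a squat load from professional rugby players in a sample that is half female.
- *Section 2.2 sides with the hypothesis.* Its wording is ambiguous.

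The sponsor could instead rewrite the hypothesis to include motion capture. That would be consistent, but it would abandon the question about mobile technology that motivates the project.

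**Conclusion.** The contradiction is real and sits in the definition of the primary prediction. It should be resolved before analysis. If 2.3 is followed, the reported accuracy describes a motion-capture-assisted method and does not answer the hypothesis. If the motion-capture reference of 4.1 is kept as well, that comparison is not independent; the isokinetic comparison is free of this second problem. The plan itself expects motion capture to improve accuracy, so the likely direction is overstatement for the modelling-plus-mobile method. No size can be given.

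The conclusion rests on the sections as worded and on the absence of any rule about which one prevails. It does not assume that the investigators intend to use Vicon data in the prediction.

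**What to change.** 1. Use one definition of the predictor in 2.1, 2.2, 2.3 and 4.1, and state in 2.2 which data enter the biomechanical analysis.
2. Prespecify that the accuracy result for the hypothesis uses app/iPhone/Apple Watch data plus the subject-specific model, with no Vicon input, compared with isokinetic tests.
3. Report the motion-capture-assisted prediction, and its paired difference from the prediction in item 2, as secondary results from the same Visit 2 and Visit 3 recordings.
4. In 4.1, do not use motion capture as a reference for any prediction that takes it as input.
5. If H:Q ratio cannot be computed without motion capture, say so and limit the conclusion about mobile technology to 1RM.

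The cost is an amendment to the wording and a second computation on existing recordings, with no added visit or measurement. The headline accuracy will probably be less favourable.

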## 3 PROJECT POPULATION AND STUDY PROCEDURES

### 3.1 Project population, inclusion and exclusion criteria

Project population: The project population are healthy adult subjects who are all participating in their own strength training program on a regular weekly basis. The primary objective is to predict changes in muscle strength (i.e. primary outcome parameters: 1RM and H:Q ratio) following different training volumes of key muscle groups associated with knee joint stability. A power analysis was conducted using statistikguru.de to assess the required sample size for the primary outcome parameter, 1RM. A Cohen's of  $d=1.5$  was assumed based on previously reported changes in absolute and relative strength following an 8-week strength training intervention in 19 professional rugby league players, with reported changes in squat 1RM pre:  $170.6 \pm 21.4$  kg, post:  $200.8 \pm 19.0$  kg,  $p < 0.001$ ; and squat 1RM/(body weight) pre:  $1.78 \pm 0.27$  kg·kg, post:  $2.05 \pm 0.21$  kg·kg,  $p < 0.001$ ; respectively [52]. Given 3 study groups, alpha was set at 0.025. With a

power of 0.9, the required sample size is 11 participants per study group for drawing statistically significant conclusions. Based on the power analysis, we aim for a total of  $n=36$  complete data sets ( $n=12$  per study group of the strength training intervention), with a sub-group of  $n=12$  participants additionally scheduled for MRI of the lower limbs at baseline.

The MRI-based assessment of muscle volume for validation of the HMF technique is analyzed independently from the strength training intervention. Thereby, the accuracy of the HMF technique is dependent on the initial generic musculoskeletal model that is used for model fitting, as well as the available subject-specific skin surface and anthropometric data. The level of significance in the difference of muscle volume between HMF and MRI is expected to vary across muscle-tendon groups, as well as between population groups and gender. In particular, no significant differences were found in the predicted volume of semitendinosus and semimembranosus as part of the hamstrings between HMF and MRI in 5 children without CP (MRI 5.1 (0.91) versus HMF 5.0 (0.30)  $\text{cm}^3/\text{kg}$ ,  $p\text{-value} > 0.05$ ) and in the predicted volume of the quadriceps, including vastus lateralis, medialis, intermedius and rectus femoris, in 6 children with CP (MRI 15.9 (3.20) versus HMF 16.5 (2.58)  $\text{cm}^3/\text{kg}$ ,  $p\text{-value} > 0.05$ ), respectively [22]. Based on previous research, it can be expected that additional consideration of somatotype from anthropometric measurements will help to improve model fit by allowing to adjust the relative thickness of the skin layer, and thus segmental inertia properties, via the HMF objective function for individual subjects. Furthermore, it is very likely that the accuracy in fitting results will be improved when fitting a generic musculoskeletal model to subjects of similar age and gender, and without significant musculoskeletal impairments, which will be the case in the present study. Further details to the MRI-based analysis are provided in Subsection 3.3.

All participants have to confirm their voluntary participation with a written informed consent before being submitted to any study procedure.

Inclusion criteria (all participants,  $n=36$ ):

- Healthy participants; and
- Age 18-40 years old; and
- No acute or chronic musculoskeletal symptoms or pain; and
- Experience with strength training (at least 1-year strength training experience with one training session per week or more); and
- Familiar with strength exercises of key muscles associated with knee joint stability.

Exclusion criteria (all participants,  $n=36$ ):

- Acute or chronic musculoskeletal pain; and/or
- Musculoskeletal surgery within the last 12 months; and/or
- Ongoing rehabilitation or treatment of musculoskeletal complaints or injury; and/or
- Neuromusculoskeletal disease (e.g. cerebral palsy); and/or
- Pregnancy.

Additional inclusion criteria (sub-group of participants,  $n=12$ ):

- No metallic implants
- Comfortable being inside the MRI tunnel for 10-15 min (no history of claustrophobia).

Justification: The design of the strength exercises and participant requirement of at least 1-year strength training experience is based on the expertise of the PI in strength training research involving healthy participants [30, 31, 38-41, 45]. The age cut-off at 40 years is defined in order to avoid co-founding factors between genders due to age-related changes of the musculoskeletal system in females following menopause, i.e. reported decline in muscle mass and strength due to a decline in oestrogen [47]. The additional inclusion criteria for the sub-group of  $n=12$

participants are to minimize image artefacts or incomplete datasets due to metallic implants or claustrophobia, as well as measurement bias in the direct assessment of muscular strength.

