#### PHASE A: Screening, informed consent & baseline measurements.

- **1st Visit:** Screening, informed consent, health- and training-related questionnaire, allocation into three study groups (Group#1: no training, Group#2: 1 training per week, Group#3: 3 trainings per week). The approximate duration of the 1st Visit is **1h**.
- **2nd Visit:** Baseline measurements. 3D body surface scan, anthropometric measurements, ultrasound, isokinetic strength tests, iPhone/watchOS measurements and optical motion capture during exercise execution. The approximate duration of the 2nd Visit is **4h**. The time between the 1st and 2nd visit is defined within two weeks of the 1st visit to fit in with the participant's schedule.
- **MRI scan** (sub-group,  $n=12$ ): An additional visit is scheduled for the sub-group of  $n=12$  participants to obtain data from MRI of the lower limbs. The scan time is 10-15 minutes, with the total duration of the visit to the MRI facilities at the SCMI being approximately **30**

**minutes.** MRI data acquisition is individually defined within two weeks of the 1st visit to fit in with the participant's schedule.

PHASE B: 8-week strength training intervention. Conduct of an 8-week strength training intervention of key muscle-tendon groups associated with knee joint stability in the training-specific setting of each participant. Participants are randomly allocated into three study groups with increasing levels of loading (Group#1: no training, Group#2: 1 training per week, Group#3: 3 trainings per week) with the same number of subjects and gender distribution in each group ( $n=12$  per group, 6F and 6M). The same guidelines for the warm-up and the type of exercises will be given prior to the intervention study to each participant. Participants are asked to record exercise load and volume as well as monitor training-related variables and 1RM using the *iOS Strength Control app*. Participants perform the strength training self-directedly in their chosen fitness/training facilities as it fits into their weekly routine. Contact to the study investigator is ensured at all times in case of questions.

PHASE C: Post-intervention measurements.

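### Training experience is named as a key baseline factor but is neither balanced at allocation nor adjusted for, and the handling of participants' own training is not stated

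*Combined protocol and SAP*

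**What the plan says.** - **Named factors (2.2).** "Key baseline factors that will likely influence the primary and secondary endpoints are strength training experience and gender".
- **Stated control (2.2, repeated in 3.3).** The eligibility criteria and the study protocol, "including a training-related questionnaire, are defined to minimize the bias of training experience".
- **Eligibility (3.1).** "Experience with strength training (at least 1-year strength training experience with one training session per week or more); and". A separate criterion asks only for familiarity with the relevant exercises. Neither years of training nor weekly frequency has an upper limit.
- **Population (3.1).** "healthy adult subjects who are all participating in their own strength training program on a regular weekly basis".
- **Assigned volumes (2.2).** "Group#1: no training, Group#2: 1 training per week, Group#3: 3 trainings per week".
- **Allocation (2.3; 3.3, Phase B).** Random, "with the same number of subjects and gender distribution in each group": 12 per group, 6 women and 6 men.
- **Timing (3.3, Phase A).** Visit 1 covers "Screening, informed consent, health- and training-related questionnaire, allocation into three study groups".
- **Analysis (4.1).** The main strength analysis is described thus: "a repeated measures analysis of variance (ANOVA) will be conducted to assess statistically significant differences between the predicted values of 1RM and H:Q ratio" and the measured values. Correlations with training-specific parameters follow, by study group. Section 2.3 lists those parameters, and training history is not among them. The paragraph on validating the host mesh fitting (HMF) technique adds analyses by gender. No covariate for experience or habitual frequency appears.

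**The concern.** The plan treats its two key factors differently. Gender is controlled in the design and examined in the analysis. Experience has an entry minimum and a questionnaire whose answers are given no use. A minimum narrows the range from below only, and a questionnaire reduces bias only if its data enter the allocation or the analysis.

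Section 2.2 commits to comparing changes in 1RM, H:Q ratio and muscle size between the three volume groups. If groups of 12 differ by chance in prior training, that difference can imitate or hide part of a volume effect, and the plan has no adjustment to separate the two.

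A second gap compounds this. Everyone enrolled already trains weekly, and the documents do not say what happens to that training during the 8 weeks. What a group label means as a change from a participant's usual routine therefore depends on an unstated rule.

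**Working it through.** **Group size.** The plan gives no figure for imbalance; the relevant plan figure is the group size. Section 3.1 derives 11 per group from d = 1.5, power 0.9 and alpha 0.025, and plans 12. The effect size reproduces: (200.8 − 170.6) / √((21.4² + 19.0²)/2) = 30.2/20.24 = 1.49. A noncentral-t calculation gives 11 per group at one-sided 0.025 and 13 at two-sided 0.025; sidedness is not stated. The point here does not depend on this. It uses only n = 12 per group.

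**Chance imbalance, two-level factor.** Assumption: half of each sex is high-experience (9 of 18), allocated at random to three groups of 6 within sex. For one sex, P(a, b, c) = C(6,a)·C(6,b)·C(6,c) / C(18,9), with a + b + c = 9 and C(18,9) = 48,620. Adding the two sexes and taking the largest minus the smallest group count gives:

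| Largest gap between two groups | Probability |
|---|---|
| 3 or more of 12 | 54% |
| 4 or more of 12 | 34% |

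The same formula with other assumed splits gives, for a gap of 3 or more, 50% if 6 of 18 per sex are high and 33% if 3 of 18 are. Balancing on sex does not remove the problem.

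**Chance imbalance, continuous factor.** The standard error of a standardised difference between two groups is √(2/12) = 0.408. Then P(|difference| > 0.5 SD) = 2·(1 − Φ(0.5/0.408)) = 22% for one pair. By simulation it is about 44% for at least one of the three pairs.

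**Effect on a group contrast.** The documents do not give the association between experience and outcome. For an assumed R² of 0.10 to 0.40, a 0.5 SD imbalance shifts an unadjusted contrast by 0.5·√R², that is 0.5·√0.10 = 0.16 to 0.5·√0.40 = 0.32 outcome SD.

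**What the assigned volume means, case 1: it replaces own training, and own training includes leg work.** Change = assigned minus habitual sessions per week. The habitual range of 1 to 4 is borrowed for illustration from the earlier app sample in 1.3.

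| Habitual | Group#1 (0) | Group#2 (1) | Group#3 (3) |
|---|---|---|---|
| 1 | −1 | 0 | +2 |
| 2 | −2 | −1 | +1 |
| 3 | −3 | −2 | 0 |
| 4 | −4 | −3 | −1 |

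Group#1 is a cut for all and Group#2 an increase for none. Group#3 alone mixes directions. With habitual frequencies 1/2/3/4 in proportions 40/30/20/10%, Group#3 is 70% increase, 20% unchanged and 10% cut. With 10/20/30/40%, it is 30%, 30% and 40%.

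**Case 2: it adds to own training.** Actual volume is then habitual plus 0, 1 or 3. A Group#1 participant who usually trains three times a week has the same actual total (3) as a Group#2 participant who usually trains twice (2 + 1). The labels no longer describe the volume received.

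**The case against.** - **Randomisation already handles prognostic factors.** In expectation it does, and chance imbalance is part of the test's error rate. A reader might infer that the group comparison is biased by design; the documents do not support that. What stands is the likely size of imbalance at 12 per group and the lack of any adjustment for a factor the plan itself calls key.
- **The primary analysis is unaffected.** Largely true. The ANOVA in 4.1 sets predicted against measured values in the same participants, so prior training hardly confounds it. The exposure is in the between-group comparison promised in 2.2.
- **The plan does address experience.** The sentence in 2.2 and 3.3 credits the study protocol and questionnaire as well as eligibility, and one year of training does exclude novices. It would be wrong to say nothing is done. What is done does not amount to minimising the bias.
- **The cut-or-increase argument rests on an unstated premise.** A reader might infer outright that Group#2 cannot be an increase for anyone, or that every group mixes people who detrain, maintain and progress. Neither follows. The first needs assigned sessions to replace own training that already includes leg work; someone training mainly the upper body could gain leg sessions in Group#2. The second, even on that premise, is true only of Group#3, and only if some participants train four or more times a week. Describing the groups as rising in load correctly orders the assigned levels.
- **Habitual volume may not be recorded.** The questionnaire's items are not listed, and 6.2 says only that the training routine will be discussed. Whether usable data exist at allocation has to be confirmed.
- **The frequencies depend on the assumed mix.** They do. With a uniform 1–4 mix, the largest gap between group means reaches 0.5 sessions per week in about 58% of simple allocations; with a 15/50/30/5% mix, about 31%.

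**Conclusion.** The point holds in a bounded form. The plan names experience as a key factor, sets only a floor for it, balances and analyses by gender alone, and gives the questionnaire no role in allocation or analysis. The stated control of this bias is therefore not delivered beyond excluding novices.

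The consequence is lower precision and possible chance confounding in the between-group comparison, not systematic bias and not a failure of the validation analysis. With half of participants in each experience level, a gap of 3 or more of 12 between two groups occurs in about 54% of sex-balanced allocations; a more uneven split lowers this, to 33% at 3 of 18 per sex. The shift of 0.16 to 0.32 outcome SD rests on the assumed R² and a 0.5 SD imbalance.

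Separately, the volume contrast is not fully defined, because the documents do not say whether assigned sessions replace or supplement own training. This should be corrected, and it does not by itself invalidate the trial.

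**What to change.** 1. Confirm that the Visit 1 questionnaire records years of strength training and habitual lower-limb sessions per week; add the items if it does not.
2. In 2.3 and 3.3, allocate by minimisation on sex plus one training factor (experience or habitual volume), with its categories fixed in advance. Minimisation avoids very small strata at n = 36.
3. In 4.1, write out the between-group comparison promised in 2.2, with years of training and habitual lower-limb sessions as prespecified covariates. Balancing on frequency alone would not capture years of experience, so both belong in the model.
4. Report each participant's assigned volume relative to habitual volume.
5. Reword the sentence in 2.2 and 3.3 to say that eligibility excludes novices and that remaining differences are handled by allocation and adjustment.
6. The sponsor should reconcile the population and eligibility text in 3.1 with Phase B in 3.3, stating how own training is handled during the 8 weeks. No training volume is proposed here.

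**Cost.** The questionnaire must be scored before allocation at the same visit, and one or two degrees of freedom are spent: for a three-group model on 36 participants, residual degrees of freedom fall from 36 − 3 = 33 to 31 with both covariates. No additional participants or visits are needed.
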